### 2.3 Study Endpoints

#### 2.3.1 Primary Efficacy Endpoints

The primary efficacy endpoint is the median reduction from baseline of urine protein to creatinine ratio (UPCR) of at least 20 % i.e. >20% by Week 12.

#### 2.3.2 Secondary Efficacy Endpoints

Secondary efficacy endpoints measured through Week 12 and End of Treatment include:

- Achievement of partial or complete remission of urine protein to creatinine ratio (UPCR)
  - Partial Remission (includes all of the following):
    - Reduction from baseline by >50% in UPCR
    - Reduction in UPCR to a level that is <3.5 g/g
    - Subject may not be a treatment Failure
  - Complete Remission (includes the following):
    - Reduction in UPCR to <0.3 g/g
    - Serum albumin within normal range
    - For patients with abnormal serum creatinine levels at baseline, return to normal levels for that age group
    - For patients with normal serum creatinine levels at baseline, final value within 20% of baseline levels
    - Subject may not be a treatment failure
- Change from baseline in UPCR over time
- Time to and proportion with achievement of partial remission during the treatment period
- Time to and proportion with achievement of complete remission during the treatment period

- Time to rescue therapy, based on Investigator or physician initiation of glucocorticoids or new immunosuppressive agents or new major treatment modalities (e.g. plasmapheresis, dialysis)

### 2.3.3 *Exploratory Efficacy Endpoints*

Exploratory Efficacy Endpoints include:

- Assessment of biomarkers associated with disease activity over time, including blood lipid profile, urinary MCP-1, and potentially other biomarkers of renal inflammation, fibrosis and injury
- Assessment of biomarkers associated with risk of severity of disease, which may include allelic variations associated with the pathogenesis and/or prognosis of FSGS such as NPHS1, NPHS2, WT-1, LAMBD2, CD2AP, TRPC6, ACTN4, INF2, APOL1
- Assessment of blood and/or urinary biomarkers associated with CCR2 biology, which may include peripheral blood leukocyte subsets and selected cytokines and chemokines
- Assessment of mechanisms by which nephrotic syndrome may potentially impact pharmacokinetics of CCX140, including assessment of CCX140 in urine
- Assessment of edema as measured by physical examination, leg circumference and body weight
- Assessment of concentration of CCX140-B in urine

### 2.3.4 *Pharmacokinetic Endpoints*

Concentrations of CCX140 will be determined in plasma from 4.0-mL blood samples collected in K2EDTA tubes according to Table 1. The following parameters will be determined, where possible:

- Cmax Maximum plasma concentration
- Tmax Time of maximum plasma concentration
- AUC0-6 Area under the plasma concentration-time curve from Time 0 to Hour 6 on Day 1, Day 29 (or Day 14 following 10 mg BID dosing), and Day 57 (or Day 14 following 15 mg BID dosing)
- AUC0-12 Area under the plasma concentration-time curve from Time 0 to Hour 12 on Day 29 (or Day 14 following 10 mg BID dosing), and Day 57 (or Day 14 following 15 mg BID dosing) with the assumption of the concentration of Time 0 being equivalent to Hour 12.
- Cmin Trough level plasma concentrations at Day 57 visit or beyond

On Days 1, 29 and 57, samples will be taken at pre-dose, 0.5, 1, 2, 3, 4, and 6 hours after dosing. The blood samples collected on the other relevant study days need to be collected prior to taking the CCX140-B dose.

Total plasma concentrations of CCX140 will be determined using validated analytical methods.

### 2.3.5 *Safety Endpoints*

Safety endpoints include:

- Adverse events
- Vital signs
- Physical Exam Abnormalities

- Electrocardiograms (ECGs)
- AIDS Clinical Trials Group Brief Peripheral Neuropathy Screening Tool (ACTG BPNST): to assess potential signs and symptoms of peripheral neuropathy that ACTG BPNST will be completed by study personnel or the study investigator as specified in the Time and Events table
- Changes in laboratory parameters including:
  - Hematology, including blood count, reticulocyte count, smear evaluation
  - Serum haptoglobin, lactate dehydrogenase
  - Serum chemistry including serum transaminases and CPK
  - Urinalysis
  - Coagulation factors (Prothrombin Time [PT], Partial Thromboplastin Time [PTT], International Normalization Ratio [INR])

### 3 STATISTICAL METHODOLOGY

#### 3.1 General Considerations

##### 3.1.1 Analysis Day

Analysis day or study day will be calculated from the date of first dose of study drug. The day of the first dose of study drug will be Day 1, and the day immediately before Day 1 will be Day -1. There will be no Day 0.

##### 3.1.2 Analysis Visits

Scheduled visits will be assigned to analysis visits as recorded in the electronic data capture (EDC) system. If a scheduled visit is not available, unscheduled and early termination visits will be assigned to analysis visits using analysis visit windows based on the actual date the assessment took place. The start day of the analysis window will be calculated as the midpoint between the scheduled assessment and previously scheduled assessment for that parameter. The end of the analysis window will be calculated as the midpoint between the scheduled assessment and the next scheduled assessment for that parameter. Where multiple measurements for a particular parameter appear within an analysis window, the scheduled visit will be used. If no scheduled visit appears in the analysis window, the result closest to the target day will be used. If equidistant and both are unscheduled and/or early termination visits, the later result will be used for the summary measure.

Though all measures may not be used in data summaries (e.g., two lab measures within the same analysis visit window), all measurements appear in the datasets and listings. For subjects where the event date is missing, the study day and analysis window will also be missing. See below for an example of analysis windows for eGFR.

Analysis Visit	Target Analysis Day	Low Analysis Day	High Analysis Day
Day 15	15	2	22
Day 29	29	23	43
Day 57	57	44	71
Week 12	85	72	99
Week 16	113	100	127
Week 20	141	128	155
Week 24	169	156	183

Week 28	197	184	211
Week 32	225	212	239
Week 36	252	240	266
Week 40	281	267	295
Week 44	309	296	323
Week 48	337	324	351
Week 52	365	352	379

### 3.1.3 *Definition of Baseline*

Baseline is defined as the last assessment prior to the first dose of study drug.

### 3.1.4 *Summary Statistics*

Categorical data will generally be summarized with counts and percentages of subjects. The denominator used for the percentage calculation will be clearly defined. Continuous data will generally be summarized with descriptive statistics including n (number of non-missing values), mean, median, standard deviation, standard error of the mean, minimum, and maximum.

### 3.1.5 *Hypothesis Testing*

Since this is a small open-label study with one treatment group, formal hypothesis testing is not applicable.

### 3.1.6 *Evaluation of Site Effect*

Due to the small sample size, site effect will not be evaluated for this study.

### 3.1.7 *Adjustments for Potential Impact of COVID-19*

As no subjects' data was impacted by COVID-19, adjustments to analyses and summaries will not be required.

## 3.2 Analysis Populations

### 3.2.1 *Intent-to-Treat (ITT) Population*

The ITT Population is defined as all subjects who have received a dose of the study drug and have at least one post-baseline efficacy assessment.

### 3.2.2 *Safety Population*

The Safety Population is defined as all subjects who have received at least one dose of study drug.

### 3.2.3 *Pharmacokinetic Population*

The pharmacokinetic (PK) population is defined as all randomized subjects who received at least one dose of study drug and have at least one evaluable PK sample. Subjects with major protocol deviation such as PK deviation or compliance issues may be excluded from the PK analyses (i.e. descriptive statistics) upon agreement with the Sponsor on case by case basis but will be listed. Values that are excluded from the analysis will be footnoted appropriately.

### 3.3 Subject Data and Study Conduct

#### 3.3.1 *Subject Disposition*

The number of subjects who were screened, who screen failed (by reason), who completed Week 12, who completed the 52 week extension study, who withdrew early from the study, along with the reasons for withdrawal, and who prematurely discontinued study treatment, along with the reasons for discontinuation, will be presented using counts and percentages.

#### 3.3.2 *Protocol Deviations*

Significant protocol deviations, i.e., those pertaining to Good Clinical Practice (GCP) violations and those that may affect the efficacy evaluation, will be captured in the Study Management System as CSR Reportable deviations. These significant deviations will be listed by category.

#### 3.3.3 *Analysis Populations*

Counts and percentages of subjects in each analysis population will be summarized based on all randomized subjects. Reasons for exclusion from each analysis population will also be summarized.

#### 3.3.4 *Demographic and Baseline Characteristics*

The following demographic and baseline characteristics will be summarized:

- Age (years)
- Sex
- Race
- Ethnicity
- Height (cm)
- Weight (kg)
- Body mass index (BMI) (kg/m^2) and BMI categories (<30 kg/m^2, ≥30 kg/m^2)
- FSGS duration (months)
- eGFR
- Proteinuria (UPCR)

#### 3.3.5 *Medical History*

Medical history including start date of FSGS diagnosis will be listed.

#### 3.3.6 *Concomitant Medications*

Concomitant medications will be coded to anatomical therapeutic chemical (ATC) class and preferred term (PT) using the WHODrug Dictionary (September 2016E B2). Prior medications are defined as any medication taken prior to the first dose of study medication (within 12 weeks of screening). Concomitant medications are defined as any medication taken on or after the first dose of study medication. A medication can be classified as both prior and concomitant if it started before or during the screening period and continued into the treatment period.

If a medication has incomplete start or stop dates, dates will be imputed to determine whether a medication should be considered prior or concomitant. See Appendix A for further information.

Prior and concomitant medications will be listed by subject including ATC class and PT based on the Safety Population.

### 3.3.7 *Concomitant Procedures*

Concomitant procedures performed during the study period will be listed.

### 3.3.8 *Study Drug Exposure and Compliance*

Days of exposure to study drug will be calculated as date of last dose of study drug – date of first dose of study drug + 1. Note that the exposure calculation is intended to describe the length of time a subject was exposed to study drug and therefore does not take study drug interruptions into account. Study drug exposure will be listed by subject for each dispense/return record including dose level. Compliance to study drug as assessed at the study site will also be listed.

## 3.4 Efficacy Assessment

Efficacy data will be summarized by randomized treatment based on the ITT Population. The primary and secondary efficacy endpoints are different than what was specified in the protocol. Partial remission, complete remission and associated endpoints (proportion and time to achievement of) as well as time to rescue therapy will not be calculated. See Section 6, Changes From Protocol-Specified Analyses for further details.

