#### 2.1.2 *Secondary Objectives*

Secondary Efficacy endpoints of this study will be assessed through Study Week 12 and through End of Treatment and include:

- Achievement of partial or complete remission of urine protein to creatinine ratio (UPCR)
- Partial Remission (includes all of the following):
  - Reduction from baseline by  $\geq 50\%$  in UPCR
  - Reduction in UPCR to a level that is  $< 3.5 \text{ g/g}$
  - Subject may not be a treatment failure
- Complete Remission (includes the following):
  - Reduction in UPCR to  $< 0.3 \text{ g/g}$
  - Serum albumin within normal range
  - For patients with abnormal serum creatinine levels at baseline, return to normal levels for that age group
  - For patients with normal serum creatinine levels at baseline, final value within 20% of baseline levels
  - Subject may not be a treatment failure
- Change from baseline in UPCR over time
- Time to and proportion with achievement of partial remission during the treatment period

- Time to and proportion with achievement of complete remission during the treatment period
- Time to rescue therapy, based on Investigator or physician initiation of glucocorticoids or new immunosuppressive agents or new major treatment modalities (e.g. plasmapheresis, dialysis)
- Changes over time in other laboratory and other parameters related to renal function, including:
  - Serum albumin
  - Creatinine
  - Cystatin C
  - eGFR, calculated by the Chronic kidney disease epidemiology collaboration (CKD-EPI) Cystatin C equation, CKD-EPI Creatinine equation, CKD-EPI Creatinine-Cystatin C equation and Modification of Diet in Renal Disease (MDRD) Creatinine equation
  - Urine albumin to creatinine ratio (UACR)
  - Total 24 hour urine protein excretion
- Quality of Life endpoints include:
  - Change in factors associated with quality of life from baseline over time as assessed using the SF-36 v2
  - Change in factors associated with quality of life from baseline over time as assessed using the EQ-5D-5L
- Safety will be evaluated via the following endpoints:
  - Adverse events
  - Vital signs
  - Electrocardiograms
  - AIDS Clinical Trials Group Brief Peripheral Neuropathy Screening Tool (ACTG BPNST)
  - Changes in laboratory parameters including:
    - Hematology, including complete blood count, reticulocyte count, smear evaluation
    - Serum haptoglobin, lactate dehydrogenase
    - Serum chemistry, expanded to include serum transaminases, CPK
    - Urinalysis
    - Coagulation factors

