### 3.4.2 *Other Efficacy Endpoints*

All other efficacy assessments will be listed. These include the following:

- Changes over time in other laboratory and other parameters related to renal function, including:
  - Serum albumin
  - Creatinine
  - Cystatin C
  - Urine albumin to creatinine ratio (UACR)
  - Total 24 hour urine protein excretion
- Quality of Life endpoints include:
  - Change in factors associated with quality of life from baseline over time as assessed using the SF-36 v2
  - Change in factors associated with quality of life from baseline over time as assessed using the EQ-5D-5L

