## 6 CHANGES FROM PROTOCOL-SPECIFIED STATISTICAL ANALYSES

There are several changes to the protocol-specified statistical analyses provided below:

- Due to the small sample size and abbreviated summary of data, no per-protocol analyses will be carried out.
- Primary endpoint analysis changed from assessing median reduction from Baseline to Week 12 of UPCR of at least 20%, to producing summary statistics for UPCR and eGFR.
- Secondary endpoint analyses have been removed. Instead this data will be listed, including:
  - Time-to-Event analysis for Partial Remission and/or Complete Remission
  - Proportion of subjects with Partial Remission or Complete Remission
  - Change from Baseline Serum Albumin over time
  - Change in UACR from Baseline over time
  - Time to investigator or physician initiation of rescue therapy including glucocorticoids, new immunosuppressive agents, or new major treatment modalities
  - Duration between achievement of remission and relapse or treatment failure
  - Changes over time in Health Quality Assessment (SF-36 v2 and EQ-5D-5L)

Rationale: Following study CL011\_140, a randomized, double-blind, placebo-controlled dose-ranging study to evaluate the safety and efficacy of CCX140-B in subjects with Focal Segmental Glomerulosclerosis (FSGS), its results did not support the development of CCX140 in FSGS. Therefore a decision was made to not continue enrollment in study CL012\_140, which also investigates CCX140 in patients with FSGS and nephrotic syndrome. In addition, the efficacy and safety summaries will be limited to specific parameters and an abbreviated CSR will be developed for this study.

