## 7 PROGRAMMING SPECIFICATIONS

Analyses will be performed using SAS® version 9.3 or higher. All available data will be presented in subject data listings which will be sorted by subject and visit date as applicable. Detailed Programming Specifications will be provided in a separate document.

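### Does the SAP contradict itself by declining to calculate remission and rescue endpoints that Section 6 says are listed and Section 2.3.2 still names?

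*SAP*

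**What the plan says.** SAP Section 3.4 (Efficacy Assessment) states that the primary and secondary endpoints differ from the protocol. It continues "Partial remission, complete remission and associated endpoints (proportion and time to achievement of) as well as time to rescue therapy will not be calculated", and refers the reader to Section 6.

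Section 6 states "Secondary endpoint analyses have been removed. Instead this data will be listed, including" and gives seven items. One is "Proportion of subjects with Partial Remission or Complete Remission". The others are time to remission, serum albumin, UACR, time to rescue, duration of remission and quality of life. The rationale follows: CL011_140 did not support development in FSGS, enrolment was not continued, and an abbreviated report will be written.

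Section 3.4.2 states "All other efficacy assessments will be listed. These include the following", then names renal laboratory parameters and the two quality-of-life instruments. It names neither remission nor rescue. Section 7 adds "All available data will be presented in subject data listings".

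Section 2.3.2, within the Study Overview, still has among the secondary endpoints "Time to and proportion with achievement of partial remission during the treatment period", the same for complete remission, achievement of either, and time to rescue. None is marked as not analysed.

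**The concern.** A proportion, a time-to-event analysis and a duration of remission cannot be listed unless someone first derives remission, and Section 3.4 says nobody will. A programmer who takes the Section 6 items as a list of outputs would be told both to produce and not to produce a remission result. Section 2.3.2 has five top-level secondary endpoints, and Section 3.4 withdraws four of them without Section 2.3.2 saying so.

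The consequence would fall on the abbreviated report. A reader who wants a remission count would have to build it from listings and make choices the SAP leaves open: 24-hour or spot UPCR away from Week 12, and which of four eGFR equations defines renal progression, since treatment failure rules out remission. Remission also mattered to conduct. Escalation depended on not having achieved and maintained at least partial remission, and remission by Week 12 was one route into the extension.

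**Working it through.** The SAP gives no figure to reproduce on this point, so the check is a comparison of sections, followed by the size of what is lost.

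**1. What the Section 6 items are.** Each is compared with Protocol Section 8.2.2 and with the two SAP sections that govern output.

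| Section 6 item | In Protocol 8.2.2 | Dropped by name in SAP 3.4 | Listed by name in SAP 3.4.2 |
|---|---|---|---|
| Time to PR/CR | yes | yes | no |
| Proportion with PR/CR | yes | yes | no |
| Serum albumin | yes | no | yes |
| UACR | yes | no | yes |
| Time to rescue | yes | yes | no |
| Duration of remission | yes | no, but needs remission | no |
| Quality of life | yes | no | yes |

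All 7 have a counterpart in Protocol 8.2.2. Three are dropped by name in 3.4, three are listed by name in 3.4.2, and one is in neither (3 + 3 + 1 = 7). No item is both dropped in 3.4 and listed in 3.4.2. The Section 6 list therefore reads as the protocol analyses being removed, and the data to be listed are the records behind them.

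**2. Whether Section 2.3.2 overrides this.** Section 2 restates the protocol. Section 2.3.1 likewise still carries the 20% median reduction, which Section 6 expressly replaces with summary statistics. Sections 3.4 and 6 both announce departures from the protocol, so they govern. Of the five top-level endpoints in 2.3.2 (achievement of PR or CR, change in UPCR, time and proportion for PR, the same for CR, time to rescue), four are dropped. Three of those four are one construct, remission, so two constructs go: remission and rescue.

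**3. Whether the components remain visible.**
- UPCR, 24-hour and morning void: summarised (3.4.1) and listed (7).
- Albumin and creatinine: listed (3.4.2).
- Rescue: concomitant medications and procedures are listed (3.3.6, 3.3.7).
- Failure and discontinuation: reasons for stopping are tabulated (3.3.1), and action taken is in the adverse event listing (3.6.1).

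At Week 12 the UPCR and laboratory components come from scheduled data, because 24-hour urine and serum chemistry are both planned at Day 1 and Day 85. On-treatment visits after Day 1 number 6 (Days 15, 29, 43, 57, 71, 85) + 10 (Weeks 16 to 52, every 4 weeks) = 16. Chemistry is planned at all but Days 43 and 71, which gives 14. Of these, 7 also have 24-hour urine (Days 15, 29, 57, 85 and Weeks 28, 40, 52). Footnote 4 of the Time and Events Table puts 24-hour collection ahead of spot and requires it to confirm response at the current dose, so the choice of sample is less open than it seems.

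**4. What a remission count would add.** SAP 3.4.3 caps the ITT Population at 13 (6 + 7). The actual N is not given, so 6 and 13 are assumed as the two planned sizes.
- Weight of one subject: 1/6 = 16.7 points; 1/13 = 7.7 points.
- Exact (Clopper-Pearson) upper 95% limit for 0 of n is 1 − 0.025^(1/n): n = 6 gives 45.9%; n = 13 gives 24.7%.
- One remission: 1/6 has 0.4% to 64.1%; 1/13 has 0.2% to 36.0%.

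The weight of one subject is a property of any proportion at this N and does not measure an error.

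**5. The partial remission threshold.** Section 2.3.2 prints "Reduction from baseline by >50% in UPCR", where 2.1.2 has at least 50%. Section 2.3.1 shows the same pattern: at least 20%, then a bare greater-than sign. A lost underline in the text copy is likely, and the threshold has no effect when remission is not derived. Nothing here rests on it.

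**The case for a change.** The strongest case for a change is that the SAP supersedes the protocol's methods, so its wording decides the output. It never says that only source data are listed, and 2.3.2 never says which endpoints are not analysed. The UPCR and laboratory components of Week 12 status are scheduled and mandatory, so a per-subject flag and a plain n/N would cost one listing and one small table. Readers could then see directly a status that guided escalation and entry to the extension.

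Part of this stands. The phrasing in Section 6 is loose, and a label in 2.3.2 would have been tidier. The rest does not carry. A label or a clarifying phrase would alter no table, listing or conclusion. Adding a remission table would reverse a scope decision that the sponsor disclosed and explained, and no error in the plan requires that. It would also need new rules for the urine sample away from Week 12, where falling back on spot urine sits badly with the footnote's requirement for confirming response, and for the eGFR equation. Protocol 8.2.2 had already ruled out formal inference on the remission and treatment failure proportions, so only description is given up.

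**Conclusion.** This is a clerical looseness inside a deliberate and disclosed reduction of scope, and no change to the plan follows. Section 3.4 and Section 6 agree once the Section 6 items are taken as the protocol analyses being removed. All seven items support that reading, and no item is both dropped in 3.4 and listed in 3.4.2. Two constructs, remission and rescue, are not derived. Their components remain in the listings and in the disposition summary, and the planned UPCR and eGFR summaries are untouched. The information given up is a descriptive proportion with N of at most 13, with an exact 95% upper limit of 24.7% even at 0 of 13.

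This rests on two assumptions: that analysts follow Section 3.4 together with Section 6 where these depart from the Section 2 overview, and that medications, procedures and reasons for discontinuation are recorded fully enough to show rescue and failure. The documents do not show whether the case report form records a declaration of treatment failure, so a reader rebuilding remission may have to infer that component.
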